9.1.3 Early Termination of Treatment

If a subject prematurely discontinues study drug treatment, an ETT Visit should be scheduled as soon as possible after the decision to discontinue treatment.

If the ETT Visit occurs 3 weeks or later following the last dose of study drug, then the ETT Visit will replace the Safety Follow-up Visit, and a separate Safety Follow-up Visit will not be required.

During the course of study conduct, if local health authorities decline to approve the TC of VX-445/TEZ/IVA, or if clinical benefit is not demonstrated for the use of the TC for the treatment of CF in specific subpopulations enrolled in this study, subjects with the relevant *CFTR* genotypes may be discontinued after communication to investigators and IRBs/IECs of the risks/benefits related to the safety and efficacy observed for the relevant subset of subjects.

If a subject withdraws from the study and also withdraws consent or assent, no further assessments will be performed. Vertex may retain and continue to use any data and samples collected before such withdrawal of consent or assent.

9.1.4 Lost to Follow-up

A subject will be considered lost to follow-up if both of the following occur:

- The subject misses 2 consecutive study visits (telephone contact and/or clinic visit) and is subsequently unable to be contacted by telephone (3 documented attempts by telephone within 2 weeks following the second missed visit)
- The subject does not respond within 2 weeks to a registered letter sent after the 3 attempted telephone contacts.

9.1.5 Completion of Study Participation

Completion of study participation for each individual subject is defined as: the Safety Follow-up Visit; or, in situations in which the ETT Visit or the Week 96 Visit replace the Safety Follow-up Visit (Section 9.1.2), the ETT Visit or the Week 96 Visit.

If subjects withdraw consent or assent, completion of study participation is defined as date of withdrawal of consent or assent, whichever is earlier (Section 9.9).

If subjects are lost to follow-up (Section 9.1.4), the date of completion of study participation will be defined as the date of last contact.

The end of study is defined in Section 13.2.8.

9.1.6 Independent Data Monitoring Committee

This study will be monitored by an independent data monitoring committee (IDMC), which will conduct periodic safety reviews of study data (Section 12.3.6.2). Procedural details of the IDMC's structure and function, frequency of meetings, and data planned for review will be included in the IDMC charter. The IDMC charter will be finalized before the first subject is enrolled.

9.2 Method of Assigning Subjects to Treatment Groups

This is an open-label study. Randomization is not required because all subjects will be treated identically in a single cohort.

9.3 Rationale for Study Elements

9.3.1 Study Design and Population

This Phase 3 study will enroll subjects who completed the last Treatment Period visit in the parent study of VX-445/TEZ/IVA and meet eligibility criteria. Results from this study will provide information on the long-term safety and efficacy of TC treatment with VX-445/TEZ/IVA in CF subjects 12 years of age or older with F/G or F/RF genotypes, as per the population enrolled in the parent study.

9.3.2 Study Drug Dose and Duration

All subjects will receive VX-445/TEZ/IVA at the same dosage as that in the parent study (Study 104).

The overall treatment duration will be 96 weeks. This duration was employed in open-label extension studies for previously approved CFTR modulators, Kalydeco and Orkambi, and is considered sufficient for the evaluation of long-term safety and efficacy.

9.3.3 Rationale for Study Assessments

The safety, efficacy, and PD assessments are standard parameters for clinical studies in drug development and are generally recognized as reliable, accurate, and relevant to the study of CF subjects. Baseline and follow-up ophthalmologic examinations (OEs) are recommended for monitoring of CF subjects <18 years of age treated with regimens that contain IVA, therefore OEs have been included in the standard safety assessments for those who were <18 years of age on the date of informed consent in the parent study.

Obstruction of airways with thick mucus, chronic bacterial infection of the airways, and inflammatory response all play a role in causing lung damage in CF. Therefore, assessments of inflammatory mediators and other blood biomarkers are included.

9.4 Study Restrictions

9.4.1 Prohibited Medications

Table 9-1 lists prohibited medications. A non-exhaustive list of study prohibitions and cautions for medication will be provided in the Study Reference Manual. Guidance for concomitant medications is provided in Section 9.5.

Table 9-1 Prohibited Medications

| Medication | Timing of Restriction | | Rationale |
|--|--|--|---|
| | Start of Restriction | End of Restriction | |
| Moderate and strong CYP3A inducers | None allowed within 14 days before the first dose of study drug on Day 1 | None allowed through completion of study participation | VX-445, TEZ, and IVA are metabolized extensively via CYP3A4. Therefore, use of moderate and strong inducers and inhibitors of CYP3A, which have the potential to alter the exposure of VX-445, TEZ, or IVA, will be prohibited. |
| Moderate and strong CYP3A inhibitors (except ciprofloxacin) ^a | None allowed within 14 days before the first dose of study drug on Day 1 | None allowed through completion of study participation | |

Table 9-1 Prohibited Medications

| Medication | Timing of Restriction | | Rationale |
|--|---|--|--|
| | Start of Restriction | End of Restriction | |
| CFTR modulators (investigational or approved), except for study drugs in the parent study and this study | None allowed within 28 days or 5 terminal half-lives (whichever is longer) before the first dose of study drug on Day 1 | None allowed until after the last dose of study drug | These agents may confound the results of this study. |

IVA: ivacaftor; TEZ: tezacaftor

^a Ciprofloxacin is not a moderate CYP3A inhibitor on the basis of results of a drug-drug interaction study conducted with IVA, a sensitive CYP3A substrate (Kalydeco [ivacaftor] US Package Insert).

9.5 Prior and Concomitant Medications

Information regarding prior and concomitant medications, including CF medications, other medications, and herbal and naturopathic remedies, will be collected in each subject's source documentation for medications taken within the 56 days before the first dose of study drug in this study through completion of study participation, as defined in Section 9.1.5.

- Subjects should remain on a stable treatment regimen for their CF through completion of study participation. Stable treatment regimen is defined as the current treatment regimen for CF that subjects have been following for at least 28 days before Day 1. Subjects should not initiate long-term treatment with new medication from 28 days before the Day 1 Visit through completion of study participation. Subjects who are taking inhaled tobramycin or other chronically inhaled antibiotics should remain on that regimen throughout the study.
- Subjects may receive doses of prednisone or prednisolone of up to 10 mg/day chronically, or up to 60 mg daily for up to 5 days.
- VX-445 may inhibit OATP1B1 and OATP1B3, which may increase the exposure of medicinal products that are substrates for these transporters. Substrates such as statins, glyburide, nateglinide, and repaglinide should be used with caution.
- IVA is a weak inhibitor of P-glycoprotein (P-gp). Administration of IVA may increase systemic exposure of medicinal products that are sensitive substrates of P-gp, which may increase or prolong their therapeutic effect and adverse reactions. Digoxin or other substrates of P-gp with a narrow therapeutic index, such as cyclosporine, everolimus, sirolimus, and tacrolimus, should be used with caution and appropriate monitoring.
- IVA may inhibit CYP2C9; therefore during coadministration with warfarin, additional monitoring of the international normalized ratio is recommended. Other medicinal products that are CYP2C9 substrates for which exposure may be increased include glimepiride and glipizide; these should be used with caution.
- Information about bronchodilator use during the study will be collected and documented. Subjects who are using a bronchodilator must have their spirometry assessments performed according to the guidelines provided in Section 11.5.1.

9.6 Administration

9.6.1 Dosing

Study drug will be administered orally. Additional information is provided in the Pharmacy Manual.

Study drug should be administered with a fat-containing meal or snack, such as a standard “CF” meal or snack, or a standard meal.

1. It is recommended that the dose be taken within 30 minutes of the start of the meal or snack.
2. Study drug will be administered as 2 fixed-dose combination (FDC) TC tablets in the morning and 1 IVA tablet in the evening. For each subject, doses of study drug should be taken at approximately the same time (± 2 hours) each day.
3. On days of scheduled visits, the morning dose of TC will be administered at the site after predose assessments have been completed. A meal or snack will be provided by the site for the morning dose of TC.
4. If a subject’s scheduled visit is to occur in the afternoon, the following guidelines should be used:
 - If the dose in the clinic will be within 6 hours of the subject’s scheduled morning dose, the subject should withhold their morning dose of TC and the morning dose of TC will be administered in the clinic.
 - If the dose in the clinic will be more than 6 hours after the subject’s scheduled morning dose of TC, the subject should take the morning dose of TC at home.
5. Subjects will be instructed to bring all used and unused materials associated with the study drug to the site; study drug will be dispensed at each visit, as appropriate.

9.6.2 Missed Doses

If 6 hours or less have passed since the missed morning or evening dose, the subject should take the missed dose as soon as possible and continue on the original schedule.

Morning dose: If more than 6 hours have passed since the missed **morning** dose, the subject should take the missed dose as soon as possible and should not take the evening dose.

Evening dose: If more than 6 hours have passed since the missed **evening** dose, the subject should not take the missed dose. The next scheduled morning dose should be taken at the usual time.

Morning and evening doses should not be taken at the same time.

9.7 Dose Modification for Toxicity

No dose modifications for toxicity are allowed. Treatment may be interrupted as outlined in Section 9.8. If any unacceptable toxicity arises, individual subjects will discontinue dosing (Section 9.1.3).

9.8 Study Drug Interruption and Stopping Rules

In subjects who have interrupted study drug for >72 hours for any reason, the investigator should resume study drug only after a thorough investigation of the cause for interruption. The

investigator will evaluate the subject's clinical stability and should consider resumption of study drug only after the subject is clinically stable and there is no comorbidity or condition that, in the opinion of the investigator, might confound the results of the study or pose an additional risk in administering study drug to the subject.

The medical monitor should be notified of an interruption of study drug that lasts >72 hours for any reason and of the resumption of study drug after such interruption. The medical monitor should be notified of any plan to discontinue study drug.

9.8.1 Liver Function Tests

The central laboratory will notify the medical monitor of alanine transaminase (ALT) or aspartate transaminase (AST) $>3 \times$ upper limit of normal (ULN) and total bilirubin $>2 \times$ ULN that are derived from centrally submitted samples.

Subjects with new treatment-emergent ALT or AST elevations of $>3 \times$ ULN, with or without total bilirubin $>2 \times$ ULN, must be followed closely, including confirmatory testing performed by the central laboratory within 48 to 72 hours of the initial finding and subsequent close monitoring of ALT, AST, and bilirubin levels, as clinically indicated.

If a subject cannot return to the site for confirmatory testing, a local laboratory may be used. Local laboratory results must be reported immediately to the medical monitor, and the subject must have the tests repeated and sent to the central laboratory as soon as possible (ideally within 48 to 72 hours).

Study drug administration **must be interrupted** immediately (prior to confirmatory testing) if any of the following criteria are met:

- ALT or AST $>8 \times$ ULN
- ALT or AST $>5 \times$ ULN for more than 2 weeks
- ALT or AST $>3 \times$ ULN, in association with total bilirubin $>2 \times$ ULN and/or clinical jaundice

A thorough investigation of potential causes should be conducted, and the subject should be followed closely for clinical progression.

Study drug administration **must be discontinued** if the following criterion is met:

- Subsequent ALT or AST values confirm the initial elevation that satisfied the interruption rule (above), and no convincing alternative etiology (e.g., acetaminophen use, viral hepatitis, alcohol ingestion) is identified, regardless of whether transaminase levels have improved.

All subjects in whom treatment is discontinued for elevated transaminases (and bilirubin, as applicable) should have these levels monitored closely until levels normalize or return to baseline.

If an alternative, reversible cause of transaminase elevation with or without increased bilirubin or clinical jaundice has been identified, study drug administration may be resumed once transaminases return to baseline or are $\leq 2 \times$ ULN, whichever is higher. Regardless of the duration of interruption, the medical monitor should be notified prior to resumption of study drug. Upon resumption of study drug, transaminases and bilirubin should be assessed weekly for 4 weeks. If a protocol-defined transaminase elevation interruption threshold recurs within 4 weeks of rechallenge with the study drug (with confirmation of the initial elevation by repeat

testing within 48 to 72 hours), then the study drug must be permanently discontinued, regardless of the presumed etiology.

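### After an interruption for raised transaminases with raised bilirubin or jaundice, the restart threshold in Protocol 9.8.1 tests transaminases only (optional patient-safety improvement)

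*Protocol*

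**What the plan says.** Protocol 9.8.1 lists three criteria for immediate interruption: ALT or AST above 8 x ULN; above 5 x ULN for more than 2 weeks; and above 3 x "ULN, in association with total bilirubin" above 2 x ULN and/or clinical jaundice. Only the third involves bilirubin or jaundice. If the elevation is confirmed and no convincing alternative cause is found, the drug is stopped for good.

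The restart rule opens "If an alternative, reversible cause of transaminase elevation with or without increased bilirubin or clinical jaundice has been identified", so it expressly covers events under the third criterion. It continues "study drug administration may be resumed once transaminases return to baseline or are" no more than 2 x ULN, taking the higher of the two. Before any restart, "Regardless of the duration of interruption, the medical monitor should be notified prior to resumption of study drug".

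Two provisions apply after restart. Transaminases and bilirubin are checked weekly for 4 weeks. If a transaminase interruption threshold recurs within those 4 weeks and is confirmed, the drug is permanently discontinued whatever the presumed cause.

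The general rule in 9.8 begins "In subjects who have interrupted study drug for >72 hours for any reason". It says that the investigator "should consider resumption of study drug only after the subject is clinically stable and there is no comorbidity or condition" which, in the investigator's opinion, might add risk. Section 9.7 adds: "If any unacceptable toxicity arises, individual subjects will discontinue dosing". Section 9.9 lets the investigator or the sponsor withdraw a subject from treatment for safety.

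For subjects taken off treatment, 9.8.1 does give bilirubin an endpoint: those stopped for "elevated transaminases (and bilirubin, as applicable) should have these levels monitored closely until levels normalize or return to baseline".

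**The concern.** The restart sentence names raised bilirubin and jaundice when it says whom it covers, then leaves both out of the recovery test. For an event that led to interruption because two abnormalities occurred together, the written threshold checks recovery of one of them.

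At stake is re-exposure to study drug while bilirubin is still above the level used in the trigger, or while the subject is still jaundiced. Whether that happens is left to case-by-case judgement, so sites could decide differently. This concerns the safety of a few individuals. It does not touch any endpoint, estimate or analysis set.

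**Working it through.** No figure in the plan needs reproducing. The check sets the interruption and restart conditions side by side and applies them to example values chosen for illustration.

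**Rules, in multiples of ULN, with an alternative reversible cause identified**

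- Third interruption criterion (9.8.1): ALT or AST > 3, and (total bilirubin > 2 or jaundice).
- Written restart threshold (9.8.1): ALT and AST <= max(baseline, 2). Bilirubin and jaundice do not enter.
- Proposed addition: bilirubin <= max(baseline bilirubin, 2), and no jaundice.

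**Cases.** The subject is first interrupted at ALT 3.5 with bilirubin 2.5 (3.5 > 3 and 2.5 > 2). Baseline ALT is at most 2, so the transaminase limit is 2. Baseline bilirubin is at most 2 except in the last row.

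| Later state | Written threshold | With addition |
|---|---|---|
| ALT 1.9, bilirubin 2.5, no jaundice | met (1.9 <= 2) | not met (2.5 > 2) |
| ALT 1.9, bilirubin 1.5, jaundice present | met | not met (jaundice) |
| ALT 1.9, bilirubin 2.0, no jaundice | met | met (2.0 <= 2) |
| ALT 1.9, bilirubin 2.2, no jaundice, baseline bilirubin 2.2 | met | met (limit max(2.2, 2) = 2.2) |

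Here, met means only that the threshold in 9.8.1 is satisfied. It does not mean that restart is cleared.

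**What else stands before restart**

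- *Interruption longer than 72 hours:* the stability and added-risk judgement in 9.8 still applies. It gives no bilirubin level.
- *Interruption of 72 hours or less:* 9.8.1 still calls for investigation of the cause, close follow-up and prior notice to the medical monitor, and the general discretion in 9.7 and 9.9 remains. The 9.8 judgement is not written for this case. The monitor is notified, not asked to approve.

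**What stands after restart.** The weekly bilirubin checks carry no action limit of their own, and the rechallenge rule is tied to a transaminase threshold. Both act after re-exposure, so neither fills the gap before it.

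**Search for a criterion elsewhere.** The COVID-19 addenda contain no restart rule. The SAP uses bilirubin only in the threshold summaries of Section 12.4. No bilirubin or jaundice condition for restart appears in either document.

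**Frequency.** The documents give none. Assuming 0 to 2 of the approximately 250 expected subjects: 0/250 = 0% and 2/250 = 0.8%.

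**The case against.** The strongest reply is that the example state is one for which the protocol never interrupts. All three criteria need ALT or AST above 3 x ULN at least, so a subject at ALT 1.9 and bilirubin 2.5 x ULN meets none of them and could stay on drug. The restart rule follows the same transaminase-based scheme. This stands: a reader might infer that the restart rule contradicts the interruption rule, and it does not. Asking for more after a combined event is a defensible clinical preference, not a correction of an error.

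A second reply is that the threshold is not the whole of the restart criteria. Section 9.1.1 refers to the resumption criteria in 9.8, which include the stability and added-risk judgement. A reader might infer that a jaundiced subject is cleared for restart. For interruptions over 72 hours the documents do not support that. Most interruptions of this kind are likely to exceed 72 hours, since confirmatory testing alone is timed at 48 to 72 hours and transaminases must then fall. Still, 9.8.1 asks for notice to the monitor however long the interruption lasted, so shorter ones are not excluded. The judgement clause also applies to transaminases, and the sponsor nevertheless wrote a numeric limit for them.

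Third, the bilirubin follow-up for discontinued subjects is a monitoring duty, not a dosing rule. That is right. It shows that the plan uses return to normal or baseline as an endpoint for bilirubin elsewhere, but not that the restart sentence is inconsistent with it.

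Finally, restart is permitted rather than required, and only where a reversible alternative cause has been identified. That narrows the affected group further.

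**Conclusion.** The point holds in a limited form. After an interruption under the third criterion with a reversible alternative cause, the only numeric restart threshold is for transaminases, and nothing in the documents requires bilirubin or jaundice to have recovered first. The remaining protection before restart is judgement and notification; after restart it is monitoring and a transaminase-based stopping rule.

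Two further inferences should be avoided. Bilirubin is not ignored after restart: it is scheduled weekly for 4 weeks. Nor are the safety conclusions at risk: the analyses are descriptive and the affected group is very small, possibly empty.

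The conclusion on the text rests on no assumption. The size rests on the assumed 0 to 2 subjects, for which the documents offer no source. This is a cheap, low-frequency patient-safety improvement: minor and optional.

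**What to change.** Add one sentence to the restart paragraph of Protocol 9.8.1: *For interruptions under the third criterion, total bilirubin must also have returned to baseline or be <=2 x ULN, whichever is higher, and clinical jaundice must have resolved.*

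The documents give no bilirubin level for restart. The 2 x ULN here is borrowed from the interruption trigger, and the sponsor's clinical team may choose another. The form copies the existing transaminase rule, so a subject whose bilirubin was already raised at baseline is not barred from restarting.

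The cost is one sentence. Total bilirubin is already in the serum chemistry panel (Protocol Table 11-1), so no new assay is needed. The downside is that a few restarts may come later. The SAP needs no change.

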9.8.2 Rash

Individuals who develop generalized rash will be monitored closely. Study drug dosing should be interrupted if a subject develops a generalized rash of Grade 3 or higher, or a rash that is considered a serious adverse event (SAE). The investigator will notify the medical monitor of any rash that results in interruption of study drug, is Grade 3 or higher (Section 13.1.1.4), or is an SAE. Investigators should consider additional evaluation including laboratory testing (e.g., complete blood count with differential, liver function test), photographs of the rash, and dermatology consultation. The investigator may consider resumption of study drug if considered clinically appropriate.

9.9 Removal of Subjects

Subjects may withdraw from the study at any time at their own request. Subjects may be withdrawn from study drug treatment at any time at the discretion of the investigator or Vertex for safety, behavior, noncompliance with study procedures, or administrative reasons.

In addition, a subject must be discontinued from study drug treatment if the subject meets any of the following criteria:

- Meets any of the stopping (discontinuation) criteria (Section 9.8)
- Becomes pregnant (Section 11.6.7.2)

If a subject does not return for a scheduled visit, reasonable effort will be made to contact the subject. In any circumstance, reasonable effort will be made to document subject outcome. The investigator will inquire about the reason for withdrawal, request that the subject return all unused investigational product(s), request that the subject return for an ETT Visit and Safety Follow-up Visit, if applicable (see Section 9.1.3), and follow up with the subject regarding any unresolved AEs.

If a subject withdraws consent or assent for the study, no further assessments will be performed. Vertex may retain and continue using the study data and samples after the study ends, and may use the samples and information in the development of the study compounds, for other drugs and diagnostics, in publications and presentations, and for education purposes. If a subject withdraws from the study, the study data and samples collected will remain part of the study. A subject will not be able to request the withdrawal of his or her information from the study data. A subject may request destruction of the samples collected from him or her during the study as long as those samples can be identified as his or her samples.

With the exception of subjects who cannot access the commercial product after regulatory approval because reimbursement by the subject's insurance carrier (whether government or private payer) is not yet available or because the subject lacks insurance coverage, subjects who become eligible to receive commercially available TC by prescription of a physician may be discontinued from study drug dosing and will complete the ETT Visit before beginning commercially available TC dosing. The Safety Follow-up Visit will not be required if the subject immediately continues on commercially available TC.

If evaluation of efficacy data from the parent study suggests that the VX-445/TEZ/IVA treatment does not provide clinically meaningful benefit for subsets of subjects included in these studies,

Vertex may recommend that subjects with relevant genotypes discontinue from the study. In addition, if local health authorities decline to approve VX-445/TEZ/IVA, or if clinical benefit is not demonstrated for the use of VX-445/TEZ/IVA for the treatment of CF in specific subpopulations enrolled in this study, subjects with the relevant *CFTR* genotypes may be discontinued after communication to investigators and IRBs/IECs of the risks/benefits related to the safety and efficacy observed for the relevant subset of subjects.

